Time to improvement in clinical status: the time (days) to the improvement of clinical status from “scale 2 to 4” to “scale 5 or above that is sustained without a drop to below 5” based on NIAID 8-point ordinal scales ([Appendix A](#)) within 28 days from randomization.

Secondary Endpoints:

- Proportion of patients who died or had respiratory failure, defined as the need for mechanical ventilation, ECMO, non-invasive ventilation, or high flow oxygen devices, at Day 29;
- Time to disease progression in clinical status: the time (days) for progression from scale 3 or 4 to scale 1 or 2, or 2 to 1, based on NIAID ordinal scale with 28 days from randomization;
- All-cause mortality at Day 15 and Day 29;
- Proportion of clinical relapse, as defined by rate of return to oxygen support for more than 1 day within 28 days from randomization after initial recovery;
- Conversion rate of clinical status on days 8 (proportion of subjects who changed from “scale 2 to 4” to “scale 5 or higher” on NIAID ordinal scale);
- Conversion rate of clinical status on days 15 (proportion of subjects who changed from “scale 2 to 4” to “scale 5 or higher” on NIAID ordinal scale);
- The discharge time
- Duration of mechanical ventilation (IMV, NIV) (days);
- Duration of pressors;
- Duration of extracorporeal membrane oxygenation (days);
- Duration of oxygen therapy (oxygen inhalation by nasal cannula or mask) (days);
- Length of hospital stay (days);
- Absolute lymphocyte count;
- D-dimer concentration in the plasma.

Exploratory endpoints:

- Effect of CD24Fc on systemic steroid usage;
- Effect of CD24Fc on cytokine levels;
- Effect of CD24Fc on lymphocyte subtype distribution.

Safety evaluation:

- Adverse events, vital signs, laboratory tests (blood routine, blood biochemistry, coagulation function, urine routine), ECG.

Study Population:

Hospitalized severe and critical COVID-19 adult patients.

Eligibility Criteria:

Inclusion criteria

- 1) Should be at least 18 years of age.

- 2) Male or female, female should have negative pregnancy test.
- 3) Diagnosed with COVID-19 and confirmed SARS-CoV-2 viral infection, prior positive viral results allowed.
- 4) Informed consent form signed by the patient or by the legally authorized representative.
- 5) Hospitalized and requiring oxygen support, NIAID 8-point ordinal score 2, 3 or 4, regardless of ARDS ([Appendix A](#)). The intubation for mechanical ventilation is within 7 days.

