2. STUDY OBJECTIVES

2.1. Primary objective:

- To evaluate the safety and efficacy of adding CD24Fc to COVID-19 best available treatment by comparing COVID-19 disease status improvement time between CD24Fc and placebo arms within 28 days.

2.2. Secondary objectives:

- Secondary objectives are to compare, for each treatment arm, proportion of patients who died or had respiratory failure (defined as the need for mechanical ventilation, ECMO, non-invasive ventilation, or high flow oxygen devices), the time to disease progression, rate of all-cause death, proportion of death or respiratory failure, rates of hospital discharge time, rate of duration of mechanical ventilation, duration of mechanical ventilation, use of pressors, rate of duration of extracorporeal membrane oxygenation, rate of duration of supplemental oxygen, the length of hospital stay, and the changes in absolute lymphocyte count and markers of inflammation.

2.3. Exploratory objectives:

- To explore the effect of CD24Fc treatment of COVID-19 on systemic steroid dosage, inflammatory cytokine changes, D-dimer level changes, lymphocyte subtype distribution and T lymphocyte activation and exhaustion markers.
- To explore the effect of CD24Fc in pulmonary function, inflammatory markers, cardiac function, liver enzymes and renal function.

2.4. Primary Endpoints:

- Time to improvement in clinical status: the time (days) required for improvement from scale 2 - 4 to scale ≥ 5 or above that is sustained without a drop to below 5 based on NIAID ordinal scales ([Appendix A](#)) within 28 days from randomization.

2.5. Secondary Endpoints:

- Proportion of patients who died or had respiratory failure, defined as the need for mechanical ventilation, ECMO, non-invasive ventilation, or high flow oxygen devices, at Day 29
- Time to disease progression in clinical status: the time (days) for progression from scale 3 or 4 to scale 1 or 2 based on the NIAID ordinal scale within 28 days from randomization.
- All cause mortality at Day 15 and Day 29
- Proportion of clinical relapse, as defined by rate of return to oxygen support for more than 1 day within 28 days from randomization after initial recovery

- Conversion rate of clinical status on Day 8 (proportion of subjects who changed from “scale 2, 3 or 4” to “scale 5 or higher” in the NIAID ordinal scale)

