4. ELIGIBILITY CRITERIA

4.1. Inclusion criteria

- 1) Should be at least 18 years of age,
- 2) Male or female, female should have negative pregnancy test,
- 3) Diagnosed with COVID-19 and confirmed SARS-CoV-2 viral infection, prior positive viral results allowed,
- 4) Informed consent form signed by patient or by a legally authorized representative,
- 5) Hospitalized and requiring oxygen support, NIAID 8-point ordinal score 2, 3, 4, regardless of ARDS (Appendix A), intubation for invasive mechanical ventilation should be within 7 days,
- 6) Women of childbearing potential, under the age of 54 years, who use adequate contraception and who agree to use adequate contraception for the duration of the study.

4.2. Exclusion criteria:

- 1) Patients who are pregnant, breastfeeding, or have a positive pregnancy test result before enrollment,
- 2) Patients previously enrolled in the CD24Fc study,
- 3) Intubation for invasive mechanical ventilation is over 7 days,
- 4) Documented acute renal or hepatic failure,
- 5) The investigator believes that participating in the trial is not in the best interests of the patient, or the investigator considers unsuitable for enrollment (such as unpredictable risks or subject compliance issues).

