10.2. Analysis Set

10.2.1. Intended-to-treat Set (ITT)

Defined as all subjects who are enrolled in the randomized trial. The ITT population will be the main analysis population for the efficacy analysis of this study. Subjects will be analyzed based on the treatment group they are assigned.

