10.4.2. Secondary efficacy endpoints

Proportion of death or respiratory failure, defined as the need for mechanical ventilation, ECMO, non-invasive ventilation, or high flow oxygen devices at D29. Cumulative number of subjects reaching the composite endpoint vs number of people in the ITT population. Chi-square test will be used to compare the difference between the two arms.

For the disease progression, during the observation period, a progression from scale 3 or 4 to scale 2 or 1, or from 2 to 1, is considered as an event. The days from the randomization to the first time point of progression will be defined as time of progression. The probability function of clinical progression will be estimated by Kaplan-Meier method. The median time and its 95% confidence interval for each group will be reported. The 95% confidence interval for the median time will be estimated using the Brookmeyer-Crowley method with log-log function conversion to achieve a normal approximation. The progression rate will be estimated by the layered Cox-Model. Cumulative progression rates estimated by the KM method for day 29 and the 95% confidence intervals will be reported.

All-cause mortality at Day 15 and Day 29: the Mantel-Haenszel stratum-weighted estimator of the risk difference will be used to compare the treatments.

Rate of clinical relapse, defined as proportion of patients who have initially reached score 5 (hospitalized, without oxygen therapy) for more than one day but subsequently become dependent on oxygen support. Since responders are not based on the randomization, a descriptive statistic will be reported and an exploratory analysis using a Chi-square test will be performed.

Improvement rate of clinical status on Days 8 and 15 (proportion of subjects with clinical improvement): percentage of subjects with clinical improvement on Day 8 or 15 in the ITT population. Chi-square test will be used to compare the difference between the two arms.

The discharge time starts from randomization to discharge. T-tests will be used to compare the differences between the two groups in completers.

Duration of each major treatment (days): Descriptive statistics will be analyzed for mechanical ventilation (IMV, NIV), extracorporeal membrane oxygenation, duration of oxygen therapy, and length of hospital stay.

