13. APPENDIX A

NIAID 8-point Ordinal Scale for COVID-19 (NCT04280705)

The ordinal scale is an assessment of the clinical status at the first assessment of a given study day. The scale is as follows:

- 1) Death;
- 2) Hospitalized, on invasive mechanical ventilation or extracorporeal membrane oxygenation (ECMO);
- 3) Hospitalized, on non-invasive ventilation or high flow oxygen devices;
- 4) Hospitalized, requiring supplemental oxygen;
- 5) Hospitalized, not requiring supplemental oxygen - requiring ongoing medical care (COVID-19 related or otherwise);
- 6) Hospitalized, not requiring supplemental oxygen – no longer requires ongoing medical care;
- 7) Not hospitalized, limitation on activities and/or requiring home oxygen;
- 8) Not hospitalized, no limitations on activities.

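### The death-or-respiratory-failure composite has no new-onset or worsening condition, so under the cumulative counting rule in 10.4.2 essentially all score 2-3 entrants are events in both arms

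*Combined protocol and SAP*

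**What the plan says.** Section 10.4.2 of the combined protocol and SAP defines the composite as "Proportion of death or respiratory failure, defined as the need for mechanical ventilation, ECMO, non-invasive ventilation, or high flow oxygen devices at D29". The next sentence gives the counting rule: "Cumulative number of subjects reaching the composite endpoint vs number of people in the ITT population". The arms are compared by a chi-square test. The synopsis and section 2.5 list the same composite first among the secondary endpoints, also labelled as at Day 29.

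In Appendix A, score 3 is "Hospitalized, on non-invasive ventilation or high flow oxygen devices" and score 2 is invasive ventilation or ECMO. Inclusion criterion 5 in section 4.1 admits patients "Hospitalized and requiring oxygen support, NIAID 8-point ordinal score 2, 3, 4, regardless of ARDS", and the synopsis agrees. The ITT set in 10.2.1 is "Defined as all subjects who are enrolled in the randomized trial", so score 2 and 3 entrants are in the denominator.

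The progression endpoint in the same section is handled differently. Its event depends on where the patient started: from score 3 or 4 down to 2 or 1, or from 2 to 1.

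**The concern.** The non-fatal part of the composite is the pair of states {score 2, score 3}, and a patient may already be in one of them at randomization. If the count runs from randomization with no reference to baseline, a patient on high flow oxygen on Day 1 is an event even if discharged well a week later. A patient ventilated on Day 1 who later dies is the same single event. Within this composite, only score-4 entrants can separate the arms.

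At stake is the plan's only combined measure of death and respiratory failure. The cumulative rule adds a block of events unrelated to treatment to both arms, which raises both proportions. It also discards any treatment effect on worsening or death in the sicker entrants. In expectation this dilutes the contrast; it does not favour CD24Fc.

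**Working it through.** The plan states no event rate, effect size or power for this composite, so there is no figure of its own to reproduce. The check is of the definition, followed by an illustration of size.

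**Matching the definition to the scale**

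| Composite component | NIAID score | Eligible at entry? |
|---|---|---|
| Invasive ventilation, ECMO | 2 | yes |
| Non-invasive ventilation, high flow oxygen | 3 | yes |
| Death | 1 | no |

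No current text limits the count to new onset, to worsening, or to score-4 entrants.

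**Consequence of the cumulative rule**

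Let f be the share entering at score 2-3, and p4 the probability that a score-4 entrant reaches the composite. Then:

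- Arm proportion = f + (1-f) × p4
- Difference between arms = (1-f) × (p4 placebo - p4 CD24Fc)

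If instead only new or worsened failure or death counts, and p23 is the probability of that in score 2-3 entrants:

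- Arm proportion = f × p23 + (1-f) × p4

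**Inputs for the illustration**

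From the documents (3.2): 270 patients, 135 per arm. Assumed, because the documents give none of them: f = 25%, 40% or 50%; p4 = 30% vs 15%; p23 = 40% on placebo against 40%, 30% or 20% on CD24Fc. The test is two-sided at 0.05.

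Power = Φ[(d - 1.96 × SE0) / SE1], where d is the difference in proportions, SE0 = √[p̄(1-p̄) × 2/135] and SE1 = √{[pC(1-pC) + pT(1-pT)]/135}. Here pC and pT are the placebo and CD24Fc proportions and p̄ is their mean.

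Worked case, f = 40%, rule as written: pC = 0.40 + 0.60 × 0.30 = 0.58; pT = 0.40 + 0.60 × 0.15 = 0.49; d = 0.09; SE0 = 0.0607; SE1 = 0.0605. Power = Φ[(0.09 - 0.1190)/0.0605] = Φ(-0.48) = 32%.

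| | f = 25% | f = 40% | f = 50% |
|---|---|---|---|
| Automatic events among 270 | 68 | 108 | 135 |
| As written, placebo vs CD24Fc | 47.5% vs 36.2% | 58% vs 49% | 65% vs 57.5% |
| Automatic share of placebo events | 53% | 69% | 77% |
| Power as written | 47% | 32% | 24% |
| Power, new or worse, p23 40% vs 40% | 55% | 37% | 26% |
| Power, new or worse, p23 40% vs 30% | 74% | 67% | 62% |
| Power, new or worse, p23 40% vs 20% | 88% | 90% | 91% |

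With no effect in score 2-3 entrants, the redefined endpoint has the same risk difference as the rule as written (9 points at f = 40%: 34% vs 25% against 58% vs 49%). The gain is then only in variance. A large gain requires the drug to reduce worsening or death in those patients.

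**The case against.** The strongest objection is that the flaw depends on one of two readings. The synopsis, 2.5 and 10.4.2 all attach Day 29 to the definition. Read as status on that day, a score 3 entrant who is home by Day 10 is not an event, and the automatic events disappear. This stands, and it makes the point conditional. It does not clear the plan, because that reading cannot be squared with a cumulative count of subjects reaching the endpoint, and 10.4.2 contains both. 'Reaching' might also be meant as entering the state after randomization, but no rule says so or defines what would be new for a score 2 or 3 entrant.

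A reader might infer that an effect on death or deterioration in the sickest patients would go unseen in the trial. The documents do not support that. As defined in 10.4.2, progression covers invasive ventilation, ECMO or death for score 3 entrants and death for score 2 entrants. All-cause mortality at Day 15 and Day 29 is analysed separately. The loss is confined to this composite.

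A reader might also take the rise from 47/32/24% to 88/90/91% power as the cost of the current rule. That rise assumes that CD24Fc halves events in score 2-3 entrants. With no effect there, the gain is about 2 to 9 points.

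Finally, being listed first does not make this a key secondary endpoint. The plan states no hierarchy or alpha allocation among secondary endpoints, and the sample size and interim analysis rest on the primary endpoint.

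**Conclusion.** The point holds conditionally and should be fixed. Under the counting rule stated in 10.4.2, essentially all score 2-3 entrants are events in both arms, the difference among score-4 entrants is scaled by (1-f), and what later happens to score 2-3 entrants does not affect the composite. 'Essentially' allows for the rare patient who steps down between the screening assessment, recorded as baseline under 7.1.12, and Day 1.

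The structure follows from the documents alone. Its size does not: f and all the event rates are assumptions, and the power figures are illustrative. The primary analysis is unaffected.

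**What to change.** Before unblinding, state one rule in 10.4.2, 2.5 and the synopsis.

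- **Preferred:** keep the cumulative count through Day 29, and define the event as death, or respiratory failure new or worse than the score at randomization. For entry score 4, that is reaching 3, 2 or 1; for entry score 3, reaching 2 or 1; for entry score 2, death. Keep all ITT subjects in the denominator and tabulate the result by entry score. State whether the screening or the Day 1 assessment supplies the entry score, since both are recorded.
- **Alternative:** if status on Day 29 is intended, say so and delete the sentence on the cumulative number reaching the composite. This also removes the automatic events.

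Either option means wording changes in three places and some programming. Scores are already recorded daily in hospital, and at study visits after discharge, so no new data are needed. The preferred option has a price: the event rate is lower, the event means something different by entry score, and it overlaps largely with the progression endpoint, differing mainly in counting a move from score 4 to score 3.

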10. STATISTICAL ANALYSIS

10.1. Sample size

In the phase III trial, the patients will be randomized at 1: 1 ratio into CD24Fc or placebo arms. It was assumed that the time to improvement the clinical status of the patients obeyed the exponential distribution, and the improvement hazard ratio (HR) was 1.54. The median time to improvement in the control group is presumed 11 days, and the median time to improvement in the treatment group is projected as 7.14 days. An interim analysis for efficacy will be performed when 70% of the required events are reached. The O'Brien-Fleming type consumption function of the Lan-DeMets algorithm is used to control the overall class I error rate $\alpha = 0.025$ (one-sided), at least 80% of the degree of confidence. At least 208 events are required to achieve 80% power. Assuming 28 days of patient follow up, the estimated number of 208 events will be reached for the final analysis approximately 28 days after the last subject is enrolled. Assuming 78% recovery rate, 270 participants will be enrolled in this trial.

The sample size was calculated on SAS 9.4 PROC SEQDESIGN.

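### Relapse is compared as a simple proportion within 28 days of randomization, so the arm that recovers sooner is observed longer and its expected relapse proportion is slightly higher even when the risk after recovery is equal.

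*Combined protocol and SAP*

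**What the plan says.** The synopsis and Section 2.5 list clinical relapse as a secondary endpoint, "as defined by rate of return to oxygen support for more than 1 day within 28 days from randomization after initial recovery". The closing date is therefore tied to randomization, not to recovery.

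Section 10.4.2 defines it as the "proportion of patients who have initially reached score 5 (hospitalized, without oxygen therapy) for more than one day but subsequently become dependent on oxygen support". It adds a caveat, "Since responders are not based on the randomization", and on that ground limits the analysis to description plus an exploratory test: "a descriptive statistic will be reported and an exploratory analysis using a Chi-square test will be performed". It does not say whether the denominator is responders or all randomized patients, although the caveat points to responders. Neither place provides a person-time rate, a time-to-relapse analysis or a fixed window after recovery.

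The two definitions also differ. In Section 2.5 the more-than-one-day condition applies to the return to oxygen. In Section 10.4.2 it applies to the time spent at score 5.

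**The concern.** Time at risk of relapse is 28 days minus the recovery time, and recovery time is what the drug is meant to shorten. If the risk of relapse after recovery is the same in both arms, the arm that recovers sooner is watched longer, so its expected proportion cannot be lower and is generally higher. The comparison leans against a drug that speeds recovery and in favour of one that slows it. The caveat about responders concerns who enters the comparison, not how long each patient is observed.

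At stake is how a listed secondary endpoint on the durability of recovery is read. Two percentages and a p-value will be interpreted even under an exploratory label.

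**Working it through.** **Inputs from Section 10.1.** The plan assumes that "the time to improvement the clinical status of the patients obeyed the exponential distribution", with medians of 11 days (placebo) and 7.14 days (CD24Fc). The stated hazard ratio reproduces: 11/7.14 = 1.54. There are 135 patients per arm and 28 days of follow-up. No relapse rate or timing is given, so those are assumptions below.

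**Step 1, recovered by day 28.** With λ = ln 2/median, λ = 0.0630 (placebo) and 0.0971 (CD24Fc) per day. F = 1 − exp(−28λ) = 82.9% and 93.4%, or about 112 and 126 responders of 135.

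**Step 2, mean days at risk per responder.** This is 28/F − 1/λ.
- Placebo: 28/0.829 − 15.87 = 17.9 days.
- CD24Fc: 28/0.934 − 10.30 = 19.7 days.
- Ratio: 1.10.

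**Step 3, relapse among responders with an equal constant hazard h.** The proportion is 1 − [λ/(λ − h)] × [exp(−28h) − exp(−28λ)]/F. Setting placebo to 10% gives h = 0.00594 per day.
- Placebo: 1 − 1.104 × (0.847 − 0.171)/0.829 = 10.0%.
- CD24Fc: 1 − 1.065 × (0.847 − 0.066)/0.934 = 10.95%.
- Ratio 1.10 (1.095 before rounding). Extra patients: 126 × 0.0095 = 1.2.

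**Step 4, relapse possible only soon after recovery.** The hazard is constant for w days after recovery and zero afterwards, equal in both arms, and set again so that 10% of placebo responders relapse. Results are by numerical integration.

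| Relapse possible within | Placebo | CD24Fc | Ratio |
|---|---|---|---|
| 3 days | 10.0% | 10.1% | 1.01 |
| 7 days | 10.0% | 10.2% | 1.02 |
| 14 days | 10.0% | 10.5% | 1.05 |
| No limit | 10.0% | 10.95% | 1.10 |

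Setting the placebo proportion at 5% or 20% hardly moves the ratios. Without a limit they are 1.10 and 1.09.

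**Step 5, the plan's 78% recovery rate.** The exponential medians imply about 88% recovery over both arms, not the 78% used to reach 270 patients. A Weibull curve with placebo median 11 days, hazard ratio 1.54 and 78% overall recovery (shape 0.62; 70.9% and 85.1% recovered) gives ratios of 1.01 (7 days), 1.03 (14 days) and 1.06 (no limit).

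**Step 6, effect on the test.** Take a constant hazard with a 14-day risk of 5% to 30%, equal in both arms. The responder chi-square at two-sided 0.05 then rejects in 5.3% to 7.6% of trials. Across the simulated scenarios, which also include early relapse, the faster arm shows the higher proportion in about 50% to 68% of trials.

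**Step 7, equal observation.** With a constant hazard and a 14-day risk of 10%, count relapse only in a fixed window, among patients who recovered early enough to have all of it. The result is 10.0% in both arms for 14 days and 5.1% in both for 7 days. The shift disappears.

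**The case against.** The plan already labels the test exploratory and the groups non-randomized, and no alpha rests on the result. On the responder denominator the excess is at most about one patient at 10% relapse. Durability is also assessed elsewhere. The primary endpoint requires improvement to be sustained, Section 10.4.1 resets the improvement date after re-hospitalization with oxygen therapy, and its third sensitivity analysis uses first improvement. Case mix among responders could bias the comparison in either direction, and the calculation does not model it. Nor does it model death or dropout after recovery. All of this stands, and it limits the weight of the point. It does not remove the unequal observation, which nothing in the plan corrects.

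A reader might make two stronger inferences, and neither is supported.
- **Per-randomized ratios.** Per randomized patient, the constant-hazard case gives 8.3% versus 10.2%, ratio 1.23, and the 7-day case gives 1.15. Most of that excess comes from more patients recovering: 93.4/82.9 = 1.127, and 1.127 × 1.095 = 1.23, while 1.127 × 1.023 = 1.15. More recovered patients means more patients who can relapse, which is a real difference per randomized patient and not a time-at-risk bias.
- **Certainty.** An effective drug need not show more relapses in this trial. What shifts is the expectation, and in a single trial the order of the arms can be close to a coin toss.

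**Conclusion.** The point holds as a minor one. With the window closing 28 days from randomization and a bare proportion compared, the expected responder relapse proportion is inflated in the faster arm by a ratio of about 1.01 to 1.10. The upper end requires a relapse hazard that stays constant for weeks. If relapse comes within a few days of recovery, the shift is negligible. The direction follows from the design, given equal relapse risk after recovery and comparable responders. The size rests on the recovery medians in Section 10.1 and on an assumed relapse rate and timing. The primary endpoint is unaffected. A change is worthwhile because the bias has a known direction and is cheap to remove, not because it threatens a conclusion of the trial.

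**What to change.** In Section 10.4.2:

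1. Reconcile the relapse definition with the synopsis and Section 2.5: whether the more-than-one-day condition applies to the time off oxygen, to the return to oxygen, or to both. State how home oxygen is counted, since scale 7 in Appendix A can include it and still ranks as improved. State the denominator.
2. Replace the chi-square with cumulative incidence of relapse from first recovery, for example at 7 and 14 days, by arm with 95% confidence intervals. Treat death without relapse as a competing event and censor at Day 29 or last contact. Keep the exploratory label.
3. Add a table of all randomized patients by Day 29 status in four classes: still recovered, relapsed, never recovered, dead. This gives a comparison that respects randomization.

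The cost is SAP wording and one table, using status data already collected. There are limits. It remains a comparison among responders, and late recoverers add little follow-up. Status is recorded daily only in hospital; after discharge it is captured at study visits (notes 5 and 7 to Table 2), so onset may be known only to within the 14 days between Day 15 and Day 29. The SAP should say how such dates are assigned.

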10.3. Analysis methods

10.3.1. General principles

The statistical analysis uses SAS9.2 (or above) version of statistical analysis software, and the analysis process is all programmed. For continuous variables, the descriptive statistics will include the mean, median, standard deviation, maximal and minimal values (mean and median will be accurate to one more digit decimal point than the original data, and standard deviation will be accurate to two more digit decimal points than the original data, and the decimal points of

the maximum and minimum values will be the same as the original data, usually up to four decimal points are kept in the statistics table). Qualitative or grade indicators are summarized using descriptive statistics including the number of subjects, percentages, and / or number of events. The detailed statistical analysis plan and method will be described in detail in the statistical analysis plan.

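### Discharge time is tested only by a t-test in undefined completers, which is not a randomized comparison and carries no descriptive label

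*Combined protocol and SAP*

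**What the plan says.** Discharge time is a listed secondary endpoint (Synopsis; section 2.5). Section 10.4.2 defines it in one sentence, "The discharge time starts from randomization to discharge", and analyses it in the next: "T-tests will be used to compare the differences between the two groups in completers".

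Four other places bear on this:

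- **Analysis sets (section 10.2).** Only ITT, PPS and the safety set are defined; there is no completer set. On ITT: "The ITT population will be the main analysis population for the efficacy analysis of this study".
- **Relapse (section 10.4.2).** "Since responders are not based on the randomization, a descriptive statistic will be reported", and the chi-square test for relapse is called exploratory.
- **Length of stay (section 10.4.2).** It gets no between-arm test: "Descriptive statistics will be analyzed for mechanical ventilation (IMV, NIV), extracorporeal membrane oxygenation, duration of oxygen therapy, and length of hospital stay".
- **Deferral (section 10.3.1).** "The detailed statistical analysis plan and method will be described in detail in the statistical analysis plan". The text available contains no further definition of completers.

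**The concern.** Completers could mean patients who were discharged, or patients who finished 28 days of follow-up. On either reading, someone who dies before discharge or is still in hospital at Day 29 has no discharge time, and section 10.4.2 assigns none. The t-test then runs on patients selected by what happened after randomization, and the drug is meant to change exactly that.

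Two distortions are possible. A drug that keeps patients alive who then leave late adds long stays to its own arm and can look slower. A drug that kills patients who would have left late removes long stays and can look faster. A real benefit can also be hidden.

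A completers analysis could serve as support for an ITT analysis. Here there is no ITT analysis of discharge time for it to support. The plan applies the right principle to relapse in the same section but not to discharge time.

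**Working it through.** **1. The plan's own figure.** Section 10.1 needs 208 events: "Assuming 78% recovery rate, 270 participants will be enrolled in this trial". 208 / 0.78 = 266.7, against 270 stated, so the number enrolled reproduces to within rounding.

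**2. Share left out (stand-in only).** No discharge distribution is given, so the improvement figures of section 10.1 are borrowed.

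- *Recovery rate:* 270 x (1 - 0.78) = 59.4, or 22%.
- *Exponential medians:* 11 days for control; for the drug, "the median time to improvement in the treatment group is projected as 7.14 days". The share not improved by Day 28 is 2^(-28/median).
  - Control: 135 x 2^(-28/11) = 135 x 0.171 = 23.1
  - Drug: 135 x 2^(-28/7.14) = 135 x 0.066 = 8.9
  - Total: 32.0 of 270, or 11.9%, split unequally (17% v 7%)

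Neither figure is a floor, because both concern sustained improvement and not discharge.

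**3. Can the plan's censoring rules rescue the t-test?** Sections 10.4.1 and 10.6 censor patients without an event at Day 29. A t-test needs an observed value for each patient and cannot use a censored time.

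**4. Illustration by simulation; all inputs are assumed.** There were 6,000 trials per scenario, with 135 per arm, whole-day exponential discharge times cut at Day 28, and a two-sided 0.05 level. The t-test was run in discharged patients. The log-rank test was run in all patients, with deaths held to Day 29. Monte Carlo SE is about 0.6 points at most. Affected patients are those who die in one arm but would survive in the other.

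| Deaths, control v drug | Control median, HR | Affected patients | t-test | All-randomized log-rank |
|---|---|---|---|---|
| 20% v 10% | 9 d, 1 | all leave Days 18-28 | slower 31.7% (mean +1.62 d) | faster 22.8% |
| 20% v 10% | 9 d, 1 | half leave late | slower 11.7% (+0.83 d) | faster 28.3% |
| 20% v 10% | 9 d, 1 | none leave late | slower 1.9% (-0.02 d) | faster 34.6% |
| 20% v 10% | 9 d, 1 | all still in hospital | slower 2.6% (-0.01 d) | faster 2.6% |
| 15% v 12% | 9 d, 1 | all leave late | slower 7.2% | faster 5.3% |
| 10% v 20% (harm) | 9 d, 1 | all leave late | faster 33.0% (-1.64 d) | slower 22.2% |
| 20% v 10% | 11 d, 1.54 | all leave late | faster 2.9%, slower 1.8% | faster 91.3% |
| 20% v 10% | 11 d, 1.54 | none leave late | faster 41.2% | faster 96.8% |
| 20% v 10% | 11 d, 1.54 | all still in hospital | faster 38.9% | faster 52.2% |

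With no treatment effect in either direction, chance alone gives about 2.5% on each side.

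**5. Equal mortality (15% in each arm, HR 1.54).** Power of the t-test against the log-rank, by control median: 7 days, 69.9% v 46.6%; 9 days, 54.7% v 56.4%; 11 days, 41.4% v 60.6%; 14 days, 27.6% v 64.6%. Neither test is uniformly more powerful.

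**The case against.** The strongest reply has five parts.

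- **The reversal is built on assumptions.** The 32% needs three things together: mortality halved, no effect on discharge speed, and every rescued patient leaving late. Section 10.1 instead assumes HR 1.54 for improvement, and at that value there is no reversal (1.8%). At HR 1.2 (median 9 days, deaths 20% v 10%; 2,000 trials) it is 11% if all leave late and 2.7% if half do. This stands: reversal is possible only in some patterns, and lost sensitivity is the likelier harm.
- **The log-rank is not uniformly better.** With equal mortality the t-test wins at a short median. Part of the log-rank's gain elsewhere reflects mortality, which is compared separately. This also stands. The reason for change is that the comparison is not randomized, and that holds whichever test has more power.
- **Exclusion is inferred.** Section 10.4.2 does not say that deaths and inpatients are dropped, and section 10.3.1 defers detail. The first half is right as to wording. But a definition of the set would not give those patients a discharge time. If completers means everyone followed to Day 29, the plan lacks a value for patients still in hospital.
- **It matters little.** Discharge time is one of 14 secondary endpoints with no alpha allocated. The primary endpoint counts discharge as improvement and is tested by log-rank. Day 8 and Day 15 improvement is tested in ITT. This stands and limits the weight of the point.
- **The missing label is editorial.** This does not stand. The plan itself gives lack of randomization as its ground for labelling relapse, and the same ground applies here.

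**Conclusion.** The concern holds and should be fixed, with modest weight. The only between-arm test of discharge time conditions on a post-randomization outcome, uses an undefined set and has no descriptive label. Its result could not be read as an effect of treatment on discharge. That conclusion follows from the text and needs no simulation.

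The size is unknown. The 12% to 22% left out rests on treating improvement as discharge. The reversal and power figures rest on assumed mortality, speed and timing, and range from no reversal to about one trial in three in the extreme cases. The primary analysis and the mortality comparison are not affected.

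**What to change.** Replace the t-test sentence in section 10.4.2, and carry the change into the SAP, with text such as:

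> Time from randomization to first discharge alive will be analysed in all ITT subjects by Kaplan-Meier and log-rank test. Subjects who die before discharge within 28 days, or who are still in hospital, will be censored at Day 29. Subjects lost to follow-up before discharge will be censored at the last date of follow-up. A death or re-hospitalization after discharge does not undo the discharge event.

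These rules mirror those of section 10.4.1 for deaths and losses. First discharge fits section 10.4.2, which has no readmission rule, and return to oxygen is already counted as relapse. If the sponsor prefers the readmission rule of section 10.4.1, the event becomes the latest discharge, and a subject readmitted with oxygen therapy and not discharged again is censored at Day 29.

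The report should state that this measure reflects survival as well as speed. Two useful refinements are to say whether discharge to any destination counts and to name an effect estimate with a confidence interval.

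**Minimum alternative:** keep the t-test, define completers, report by arm how many were left out and why, and label the result descriptive, as is done for relapse.

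**Cost:** one short paragraph and routine programming; no new data.
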